5.5.1. Analysis of Progression-free Survival and Overall Survival

Progression-free survival and overall survival will be measured using the Kaplan-Meier method. The survival function S(t) will be the likelihood of event of interest (progression or death respectively) not occurring before the date t. This function will be represented graphically with a survival curve.

These analyses will be carried out as shown in the table below:

	Progression-free survival	Overall survival
Start date	Date of starting (the treatment patient inclusion) of the target	
Date of event	Date of progression or death when receiving the main treatment at the time of inclusion	
Right censoring	Patients without an event when receiving the main treatment at the time of inclusion or lost to follow-up will be censored at the last recorded time to progression or the last tumour assessment, last disease assessment in the early study completion form, when receiving the main treatment at the time of inclusion. For patients without a tumour assessment but with a clinical assessment, the date of the tumour assessment visit will be used in the PFS analysis. If patients have both a	Patients with no event or lost to follow-up or alive at the end of the study will be censored at their last follow-up date (last follow-up date or last news).

Progression-free survival	Overall survival
tumour and clinical	
assessment, the maximum	
time between the date of the	
visit and the assessment date	
will be used in patients with	
no disease progression.	
When there is no tumour or	
clinical assessment date,	
patients will be censored	
using the treatment	
discontinuation date.	

Progression: information obtained from the "tumour assessment" section, tumour assessment visit or the "disease progression" section in the early study completion form or in the "treatment discontinuation" section if the main treatment is discontinued for disease progression.

Death: information obtained from the "patient status" section in the early study completion form or in the "outcome" section of the adverse event record page.

In the progression-free survival analysis, the first progression when receiving the main treatment at the time of inclusion will be used, either radiological progression or clinical progression if this occurs first.

The following details will be presented in summary tables:

- Number of patients;
- Number of events (with details of progression/death);
- Number of right censors (with details of patients who are lost to follow-up, no disease progression/death);
- Survival (in months): median (+95% CI), Q1 (+95% CI), Q3 (+95% CI), minimum, maximum;
- Estimated survival rate at a specific time (for example 6 months, 1 year and 2 years): number of subjects at risk, survival rate at each time.

These survival rates will be estimated and described in each of the following groups and subgroups:

- Targeted therapies group (with an estimate in the Everolimus and Sunitinib subgroups);
- Other treatments group (with an estimate in the chemotherapy, somatostatin analogs, interferon alpha and metabolic radiotherapy subgroups).

Handling of truncation/left censoring:

The study includes a retrospective and/or prospective data collection period depending on whether the patient is prevalent or incident in terms of his/her tumour treatment at the time of inclusion into the study.

The time to event of interest ("survival" time) or censoring if no event occurs (right censoring) will be based on the treatment line start date at the time the patient was included into the study.

As a result, when patients are recruited into the study, those patients who have already died on treatment could not be included, whereas patients who were still alive on treatment were included. This is left truncation.

In addition, the prevalent patients included could progress before inclusion into the study and not stop the treatment started or ongoing at the time of inclusion. This progression could not be identified and is a left censoring.

In practice, after disease progression on a given treatment, the treatment is changed. As a result, prevalent patients we observed on a given treatment at inclusion could not by definition experience disease progression.

As a result, we also do not see patients on a given treatment at inclusion who progressed on the same treatment prior to entering the study and we therefore deem these cases to be left truncations.

The distribution of an estimator which is both left-truncated and right censored can be estimated using the estimator of Kaplan and Meier (Klein and Moeschberger, 1997). The likelihood of conditional survival will be estimated as $S_a(t) = \Pr{[X > t \mid X \ge a]}$. Occurrence of an event will be studied over time t (the time since the start date) conditional on being free of this event at study entry where a represents the time between the start date and inclusion into the study. This is estimated as follows:

$$\widehat{S_a}(t) = \prod_{a \le t_i \le t} \left\{ 1 - \frac{d_i}{Y_i} \right\}, t \ge a$$

where d represents the number of events and Y represents the risk set

In addition, the Kaplan-Meier estimator does not work well when the size of the risk set is extremely small. This may occur at the end of the curve when right censorings are present and also at the start of the curve if left truncation of data occurs. This latter situation confers early instability in the point estimator of the survival function which may propagate throughout the entire curve. Lai and Ying (1991)³ suggested a solution to this problem by a slight modification of the Kaplan-Meier estimator where events are ignored when the risk set is small:

$$\widehat{S_a}(t) = \prod_{\alpha \le t_i \le t} \left\{ 1 - \frac{d_i}{Y_i} I[Y_i \ge cn^{\alpha}] \right\}, t \ge \alpha$$

where I represents an indicator, n represents the population size and c and α represent constant values. These constant values are used to define a minimum risk set size below which the events are not counted. This minimum risk set size is defined in terms of the size n of the study population. As the sizes of the subgroups we wish to compare in the OPALINE study are variable, the constants will be set arbitrarily to ensure that the minimum risk set size is equal to 5 for all subgroups. The method proposed by Lai and Ying therefore will only be effective for portions of the Kaplan-Meier curve in which the risk set does not exceed 5 patients for all the subgroup analyses.

The following analyses will be performed:

- Survival analyses (OS/PFS) for all patients with a Kaplan-Meier estimator using right censoring and left truncation (main analysis) by the PROC PHREG SAS® procedure.
- Subgroup survival analyses (OS/PFS) with a modified Kaplan-Meier estimator using right censoring and left truncation, stabilising the estimates when small samples are present (Lai and Ying method).
 - Targeted therapy vs other treatments;
 - Everolimus vs sunitinib;
 - Chemotherapy vs somatostatin analogs vs metabolic radiotherapy.

This analysis will be performed using the SAS® PROC HPSEVERITY procedure.

• Supportive survival analyses (OS/PFS) overall and by targeted therapy vs Other treatments subgroups in incident patients by the Kaplan-Meier estimate using right censoring (conventional analysis using PROC LIFETEST).

Planned visits:

The primary endpoint analysed is the overall survival rate and the progression-free survival rate at 24 months after starting treatment. A follow-up of at least the 24 month is therefore expected for all patients. Eight visits are possible in the eCRF. If the eighth study visit was carried out before 24 months, a further visit must be recorded in the eCRF to reduce the right censoring.

All of the visits (including those after follow-up for 2 years) will be taken into account in the statistical analyses.

Handling of missing data:

For survival analyses, missing data due to study drop outs may give rise to bias in the results. In order to reduce this bias, particular attention will be paid to collecting data on disease progression in the study patients.

Patients lost to follow-up without a declared event at last news in these analyses will be censored at their last follow-up time.

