3.2. Secondary objectives

This study will also enable us to meet the following secondary objectives:

- To describe the characteristics of the population of adult patients treated for a welldifferentiated, unresectable or metastatic, progressive pancreatic neuroendocrine tumour
- To describe the management of patients with well-differentiated, unresectable or metastatic, progressive pancreatic neuroendocrine tumours and treated with targeted therapies and other treatments (types of treatment, treatment regimens and prescription modalities)

This is a national observational, descriptive, prospective (partially retrospective), multicentre study carried out in France in adult patients treated for a well-differentiated, unresectable or metastatic, progressive pancreatic neuroendocrine tumour.

The study will be carried out in sites involved in the management of neuroendocrine tumours of the pancreas.

These sites will be identified from a database of doctors specialised in oncology, gastroenterology and endocrinology built up as part of this study by the two sponsors. Patients who meet the eligibility criteria will be invited to enrol in the study until the required number is met, and each patient may only be enrolled once in the study. The patient's therapeutic management will not be altered by taking part in the study and it will follow the recommendations made in a Multidisciplinary Team Meeting (MDTM) in accordance with good practice guidelines.

The inclusion phase is 28 months and will enable us to prospectively include patients seen for a consultation or hospital admission during the inclusion phase and treated by targeted therapies (Everolimus or Sunitinib) or by another treatment (one of those defined as part of this study: chemotherapy somatostatin analogues, radionuclide therapy or interferon alpha), for which the following apply:

- Treatment is started as first, second, third or fourth line treatment at the time of enrolment in the study with a change of treatment line being defined as a change of drug or combination thereof (incident cases)
- The treatment ongoing at inclusion was started as a first, second, third or fourth line therapy prior to enrolment in the study as long as treatment was started at the same site that is enrolling the patient in the study (prevalent cases)

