4.3. Analysis Sets

4.3.1. Patient Sets

- Non-included patients: all patients who are not included in the study (as recorded in the non-inclusion register).
- Included patients: all patients included in the study.
- Safety analysis set: all patients included in the study who received at least one dose of the documented treatment (the treatment start date must be entered) in the study (targeted therapy or other treatment). If the patient is prevalent, the treatment must

still be ongoing at the time of inclusion in the study and if the patient is incident, the treatment must be started at or after inclusion in the study.

• Reference set (Full Analysis Set): patients included who meet the eligibility criteria and have received at least one dose of the treatment documented during the prospective follow-up period (the treatment start date must be completed and the treatment stop date must be after the date of inclusion if the start date is prior to the date of inclusion) in the study (targeted therapy or other treatment). Patients with no follow-up data will be excluded from this population.

Two treatment groups will be analysed: the "targeted therapy" with two subgroups, everolimus (AFINITOR®) and sunitinib (SUTENT®); and an "other treatments" group with four subgroups: chemotherapy, somatostatin analogs, interferon-alpha and metabolic radiotherapy.

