5.5. Analysis of the Primary Objective

The following parameters will be analysed in the reference set in order to meet the primary objective of the study:

• Progression-free survival at 2 years when receiving the main treatment at the time of inclusion. Progression-free survival is defined by the time between starting treatment (the sequence ongoing at the time of patient inclusion into the study) and the date of

first documented disease progression or all-cause death when receiving the main treatment at the time of inclusion.

- Overall survival rate at 2 years. Overall survival is defined by the time between starting treatment (the sequence ongoing at the time of patient inclusion into the study) and all-cause death.
- Treatment safety (targeted therapies and other treatments) during the prospective period of the study described in terms of treatment discontinuations and the reasons for these, adverse events (graded according to CTCAE version 4.0, May 2009) and any complications of these adverse events. This analysis is described in Section 5.7.

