6.1.3. Left Truncation and Left Censoring

Left truncation bias is present for prevalent patients who started ongoing treatment prior to inclusion into the study because of the impossibility of including patients who have died into the study. The prevalent patients also exhibit left censoring bias because of the lack of retrospective collection of tumour assessment data.

These sources of bias are taken into account in the overall survival analysis and progression-free survival analysis using the statistical method described in Section 5.5.1.

Incident patients contribute to the survival curve from their baseline date. Conversely, prevalent patients are only at risk of developing an event from their inclusion into the study onwards and therefore do not contribute to the survival curve from their baseline date, although do contribute from a later date after their inclusion into the study. All patients from the reference set will therefore be taken into account into the survival analysis although patients whose treatment started two years before the beginning of the study will only be included after a two-year follow-up period and will therefore not be included in the estimation of the two-year survival rate. This is a limitation of the study.

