9.3.9. Supportive Analyses

Table 14.2.2.9.1: Analysis of Progression-Free Survival – Reference Set – Overall and Targeted Therapies Vs Other Treatments Group

Figure 14.2.2.9.1: Analysis of Progression-Free Survival – Reference Set – Overall and Targeted Therapies Vs Other Treatments Group

Table 14.2.2.9.2: Analysis of Progression-Free Survival – Incident Patients – Reference Set – Overall and Targeted Therapies Vs Other Treatments Group

Figure 14.2.2.9.2: Analysis of Progression-Free Survival – Incident Patients – Reference Set – Overall and Targeted Therapies Vs Other Treatments Group

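### Late entry corrects 2-year OS only for selection on being alive, but prevalent patients had to be still on the line; SAP 6.1.3 overclaims, and the planned incident-only OS check has no output

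*SAP*

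**What the plan says.** **Endpoint.** SAP 5.5: "Overall survival is defined by the time between starting treatment (the sequence ongoing at the time of patient inclusion into the study) and all-cause death". Deaths after the line has ended therefore count. SAP 5.5.1 (planned visits) makes the 24-month OS rate part of the primary endpoint.

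**Who enters as a prevalent patient.** The Protocol's design text after section 3.2 says: "The treatment ongoing at inclusion was started as a first, second, third or fourth line therapy prior to enrolment in the study". SAP 4.3.1 repeats the condition for the reference set, on which OS is analysed: "the treatment stop date must be after the date of inclusion if the start date is prior to the date of inclusion". For the safety set, a prevalent patient's treatment must "still be ongoing at the time of inclusion in the study and if the patient is incident" other timing applies.

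**Method.** SAP 5.5.1 recognises that "those patients who have already died on treatment could not be included, whereas patients who were still alive on treatment were included", and also that patients who progressed on the line before entry are not seen, since treatment is then changed. It treats both as left truncation. Its estimator conditions each patient on being free of the analysed event at entry. SAP 6.1.3 concludes: "These sources of bias are taken into account in the overall survival analysis and progression-free survival analysis".

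**Supportive check.** SAP 5.5.1 plans "Supportive survival analyses (OS/PFS) overall and by targeted therapy vs Other treatments subgroups in incident patients". In SAP 9.3.9 the incident-patient output is "Table 14.2.2.9.2: Analysis of Progression-Free Survival" with its figure. There is no OS counterpart.

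**The concern.** A delayed-entry Kaplan-Meier is valid for OS if a patient who enters at time *a* after starting the line has the same later death hazard as everyone alive at *a*. That holds when entry depends only on being alive. Here entry also depends on not having stopped the line. If patients who leave a line, mostly through progression, die faster than those still on it, late entrants are a favourable selection of survivors. They dilute the risk set with low-hazard person-time, and the OS curve sits too high.

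The error is systematic and does not shrink with sample size. It grows with the prevalent share, so it could also differ between the targeted-therapy and other-treatments groups, which are tabulated side by side.

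The Lai and Ying modification used in subgroups deals with instability in small risk sets, not with this selection. PFS on the line is much less affected, because being on the line at entry is close to being event-free.

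**Working it through.** **1. The plan's own precision.** SAP 4.2 uses 1.96 × √(0.5²/n). This gives 1.96 × √(0.25/150) = 0.080 and 1.96 × √(0.25/75) = 0.113, as stated. The documents give no figure for the bias, the prevalent share or the start-to-inclusion time, so everything below is illustrative.

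**2. Entry condition against estimator.** For OS the estimator assumes alive at *a*. The reference set requires alive *and* still on the line at *a*. The two agree only if leaving the line carries no information about later death.

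**3. Three-state model (on line, off line, dead), central case.** Assumed: median time on the line 12 months; off-line death hazard 4 times the on-line hazard; rates set to a median OS of about 38 months (the Protocol's introduction cites 38 months for pNET overall; using it from line start is an assumption). Per month:
- exit from the line, r = ln 2/12 = 0.0578, of which death on the line m₀ = 0.0072 and leaving alive λ = 0.0506
- death off the line, m₁ = 0.0289

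True survival is S(t) = e^(−rt) + [λ/(r − m₁)] × [e^(−m₁t) − e^(−rt)].

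At 24 months: 0.250 + 1.752 × (0.500 − 0.250) = 0.688 (0.687 with unrounded rates).

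At 12 months: S = 0.500 + 1.752 × (0.707 − 0.500) = 0.863, so 0.363/0.863 = 42% of those alive are off the line. Their average death hazard is 0.58 × 0.0072 + 0.42 × 0.0289 = 0.0163. A prevalent patient entering at month 12 has hazard 0.0072, yet is used to represent that whole group.

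With 50% prevalent and start-to-inclusion times uniform over 24 months before selection, the delayed-entry estimate is 71.0%, or +2.3 points. In simulations with n = 150, the incident-only Kaplan-Meier gives 68.7%.

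**4. Control.** If prevalent patients need only be alive at inclusion, the same estimator is off by 0.0–0.1 points. The extra entry condition is therefore the cause.

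**5. Sensitivity: bias in points for 24-month OS** (12 months on the line, 24-month window)

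| Off/on death hazard ratio | 25% prevalent | 50% | 75% |
|---|---|---|---|
| 0.5 | −0.5 | −1.1 | −1.7 |
| 1 | 0.0 | 0.0 | 0.0 |
| 2 | +0.6 | +1.2 | +2.0 |
| 4 | +1.1 | +2.3 | +3.6 |
| 8 | +1.4 | +3.0 | +4.8 |
| 4, shared frailty (variance 0.5) | +1.6 | +3.4 | +5.4 |
| 8, shared frailty (variance 1) | +1.9 | +4.1 | +6.8 |

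**6. A second set of inputs.** Assumed: line median 8–14 months, post-line survival median 12–27 months, 10% of line ends being deaths, starts spread over 36 months. The overstatement is about 1–2 points at 30% prevalent, 2–4 at 50% and 3–6 at 70%. Example (11 and 18 months, 70% prevalent): true 62.8%, delayed entry about 67%, incident-only 62.6%, with 95% interval coverage of 86% for delayed entry. Across settings, coverage is 93–95% at 30% prevalent, 88–96% at 50% and 79–92% at 70%.

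**7. Outputs.** The OS shells are Tables 14.2.1.5–14.2.1.8 and 14.2.2.7.1–14.2.2.7.18. None is restricted to incident patients. Section 9.3.9 and the list in SAP section 7 carry supportive shells for PFS only.

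**The case against.** **Direction.** A reader might infer that OS is certainly too high in every group. The documents do not support that. The upward sign needs higher mortality after leaving the line, or frailty shared by progression and death. The CRF also lets a line end because a cumulative dose was reached, at a scheduled stop, or for optimum response. Such endings fit fixed-course treatment, and the bias there could be nil or negative. This stands.

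**Size and coverage.** The prevalent share and the survival inputs are assumed. The largest figures in step 6 come from short survival and 70% prevalent; settings with a median OS of 36–44 months give 1–2 points at 30–50% and about 3 at 70%. The central +2.3 is well inside the planned ±8 points. A general claim that the interval under-covers fails at low prevalent shares. This stands too, although a systematic error is not excused by being smaller than the random one.

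**Missing analysis.** A reader might infer that incident-only OS was never planned. It is planned in 5.5.1; only its outputs are missing.

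**Switching to the incident-only rate.** It is tempting to quote that rate whenever the two differ. They will nearly always differ by chance, so the headline would become data-dependent. Accuracy would usually suffer as well: the all-patient estimate had the lower root mean square error in 14 of 15 simulated settings (for example 6.3 against 6.8 points at 11 and 18 months, 70% prevalent). Nor is the incident-only rate guaranteed unbiased. The reference set drops patients without follow-up data, which could remove early deaths depending on how the rule is applied.

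**Stakes.** The objective is descriptive, and SAP 6.4 says treatment comparison is not strictly appropriate. That limits the between-group argument but not the accuracy of the OS rate itself.

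**Conclusion.** The point holds for OS. The estimator allows for selection on survival, the entry rule adds selection on still being treated with the line, and SAP 6.1.3 wrongly presents the whole as handled. That follows from the text alone.

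The likely effect is an overstated 2-year OS, because the SAP itself says treatment is changed after progression. The direction is an expectation, not a certainty, and is weakest in groups where lines end by schedule. Under assumed inputs the overstatement is about 1–3 points at 30–50% prevalent (up to about 4 with short survival or shared frailty) and about 3–6 at 70%. Under-coverage is a concern mainly at high prevalent shares. Confidence is high on the mechanism and the missing outputs, and moderate at most on the size and on the direction by group.

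The OS analyses in SAP 5.9.8 use the same method and rest on the same assumption.

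**What to change.** 1. In SAP 6.1.3, state that late entry for OS corrects only for selection on survival, that selection on still being on the line remains, and that the expected direction is upward where mortality is higher after leaving the line.
2. Add incident-only OS tables and figures to 9.3.9 and to the list in section 7: overall, and targeted therapies against other treatments, as 5.5.1 already promises.
3. In Tables 14.2.1.5 and 14.2.1.6, print beside the all-patient 24-month OS rate the incident-only rate with its 95% CI, the prevalent share and the start-to-inclusion time.
4. Keep the pre-specified all-patient analysis as the main one, and do not switch to the incident-only rate according to the observed difference.

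The cost is some SAP wording and a few more outputs from data already held. The incident-only interval will be wider: by the SAP formula about ±11 points with 75 incident patients, against ±8 with 150.

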Using a similar template:

Table 14.2.1.3: Analysis of Progression-Free Survival – Reference Set – Targeted Therapy Groups

Table 14.2.1.4: Analysis of Progression-Free Survival – Reference Set – Other Treatments Groups

Table 14.2.1.5: Analysis of Overall Survival – Reference Set – Overall

Table 14.2.1.6: Analysis of Overall Survival – Reference Set – Targeted Therapies Group Vs Other Treatments

Table 14.2.1.7: Analysis of Overall Survival – Reference Set – Targeted Therapies Groups

Table 14.2.1.8: Analysis of Overall Survival – Reference Set – Other Treatments Groups

^{*} Event related to main treatment at inclusion.

Programmer note:

- The Kaplan-Meier curves associated with the analyses.
- Show the 95% confidence interval (log-log transformation) of the survival function for the total population analyses.

Table 14.2.1.9: Best Overall Response to the Main Treatment At Inclusion – Reference Set – Analysis Based on Targeted Therapies and Other Treatments

		Targeted therapies (N=XX)	Other treatments (N=XX)	Total (N=XX)
Best overall response	N	XX	XX	XX
•	Missing data	XX	XX	XX
	CR	XX (XX.X%)	XX (XX.X%)	XX (XX.X%)
	PR	XX (XX.X%)	XX (XX.X%)	XX (XX.X%)
	Clinical response	XX (XX.X%)	XX (XX.X%)	XX (XX.X%)
	SD	XX (XX.X%)	XX (XX.X%)	XX (XX.X%)
	PD	XX (XX.X%)	XX (XX.X%)	XX (XX.X%)

Using the same template:

Table 14.2.1.10: Best Overall Response with Main Treatment at Inclusion – Reference Set – Analysis by Treatment Subgroup

Table 14.2.1.11: Best Overall Response During Follow-Up – Reference Set

		Total (N=XX)
Best overall response	N	XX
•	Missing data	XX
	CR	XX (XX.X%)
	PR	XX (XX.X%)
	Clinical response	XX (XX.X%)
	SD	XX (XX.X%)
	PD	XX (XX.X%)

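### In the small other-treatment subgroups, the minimum risk set of 5 also drops late events, so mean 24-month PFS is overstated when PFS is short; print the unmodified estimate and the count of ignored events beside it

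*SAP*

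**What the plan says.** SAP 5.5.1 notes that Kaplan-Meier performs badly when the risk set is very small: "This may occur at the end of the curve when right censorings are present and also at the start of the curve", the start being a problem under left truncation. Its stated reason for changing the estimator is the start: "This latter situation confers early instability in the point estimator of the survival function which may propagate throughout the entire curve". The remedy is the Lai and Ying indicator, which keeps an event only if the risk set Y is at least c·n^α: "These constant values are used to define a minimum risk set size below which the events are not counted". For this study "the constants will be set arbitrarily to ensure that the minimum risk set size is equal to 5 for all subgroups". A later sentence says that the method acts only on portions of the curve "in which the risk set does not exceed 5 patients for all the subgroup analyses".

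The modified estimator applies to targeted versus other treatments, to everolimus versus sunitinib, and to "Chemotherapy vs somatostatin analogs vs metabolic radiotherapy". The last set is reported in "Table 14.2.1.4: Analysis of Progression-Free Survival – Reference Set – Other Treatments Groups". The template, Table 14.2.1.2, prints event counts, the median, and the rate with N at risk at six times up to 24 months. Its footnote names the Lai and Ying method.

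On numbers, SAP 3.3 sets minima of 75 for targeted therapies overall and 35 each for sunitinib and everolimus, and a maximum of 75 for other treatments. Protocol section 10 gives at least 75 for other treatments. No minimum is set for any single other-treatment subgroup. Protocol 8.3.2.1 allows estimates in those subgroups only where numbers are large enough; SAP 5.5.1 omits that condition.

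**The concern.** The instability that SAP 5.5.1 argues from is early, but the indicator works at every time. Late in follow-up, when few patients remain, each further progression or death is ignored and the curve stays flat. In a small subgroup that plateau can be produced by the rule and be read as durable disease control.

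The 24-month PFS rate belongs to the primary objective, and Table 14.2.1.4 reports it by treatment. No unmodified estimate is planned for these whole subgroups, and no planned output counts the ignored events.

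**Working it through.** **The plan's own figure.** SAP 4.2 gives the precision of S(t) at the median as 1.96 × √(0.25/n): 0.080 at n=150 and 0.113 at n=75. Both reproduce. The table stops at n=75 and uses the ordinary variance formula, so it says nothing about the threshold in smaller subgroups.

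**Direction.** Each ignored factor (1 − d/Y) is at most 1. Replacing it by 1 can only raise the curve or leave it unchanged.

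**Floor.** With complete data, no delayed entry and no ties, the counted factors run from Y=n down to Y=5: (n−1)/n × … × 4/5 = 4/n. That is 0.40 at n=10, 0.27 at n=15, 0.20 at n=20 and 0.11 at n=35. Ties can break the floor: two events together at Y=5 give 3/n. Day-15 date imputation (SAP 4.5) can create ties.

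**Exact bias, complete data.** The modified 24-month estimate is max(4, K)/n, where K is binomial (n, S24). Bias is E[max(4, K)]/n − S24, here in points for assumed exponential medians:

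| n | 12 months (S24 0.25) | 24 months (S24 0.50) |
|---|---|---|
| 10 | +16.0 | +2.4 |
| 15 | +5.3 | +0.1 |
| 20 | +1.7 | 0.0 |
| 25 | +0.5 | 0.0 |

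**With censoring and delayed entry (simulation).** The documents give no subgroup size, median PFS, censoring rate or prevalent share, so all are assumed: exponential PFS, 0-50% prevalent entering 0-24 months after treatment start, and censoring of 1% or 3% per month (1 − 0.99^24 = 21% and 1 − 0.97^24 = 52% by 24 months). For a median of 11 months the true rate is 0.5^(24/11) = 0.22. Mean estimates:

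| n | Modified (Y<5 ignored) | Unmodified |
|---|---|---|
| 10 | 0.46-0.60 | 0.21-0.23 |
| 15 | 0.30-0.41 | 0.21-0.23 |
| 20 | 0.24-0.35 | 0.21-0.23 |
| 25 | 0.22-0.30 | about 0.22 |

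The n=10 row depends most on the entry pattern; one pattern at 3% per month reached 0.70. With a median of 24 months (true 0.50), the bias is about 0-3 points at n=20 but still about 6-19 points at n=10.

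**Which events are ignored.** Call an event early if it precedes the first time the risk set reaches 5. At 11 months and 3% per month, n=15 loses 0.00-0.06 early and 1.67-1.93 late events per data set; n=20 loses 0.00 early and 0.91-1.36 late. With 75-90% prevalent, early losses rise to 0.42-0.73 (n=15) and 0.14-0.44 (n=20), but late ones still predominate.

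**RMSE at 11 months, modified vs unmodified.**

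| n | 1% per month | 3% per month |
|---|---|---|
| 15 | 0.112-0.126 vs 0.114-0.119 | 0.194-0.233 vs 0.129-0.140 |
| 20 | 0.079-0.085 vs 0.098-0.101 | 0.108-0.149 vs 0.110-0.121 |
| 25 | 0.071-0.078 vs 0.086-0.092 | 0.086-0.108 vs 0.096-0.109 |

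**Boundary.** The formula, and the sentence on events below the minimum, count an event at Y=5; the other sentence implies that it is ignored. Ignoring it would raise the floor to 5/n and the n=20 mean at 3% per month to 0.34-0.40.

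**Plausible sizes.** Seventy-five patients make 75/4 = 18.75 per subgroup if spread evenly over four, or 75/3 = 25 over the three given the modified estimator (interferon alpha is not in that list). Either side of 20 is possible.

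**The case against.** The strongest reply is that the threshold does what it was chosen for: it accepts bias to gain stability. That stands in part. At 1% censoring per month its RMSE is about equal to the unmodified estimator's at n=15 and lower from n=20. At 3% it is worse at n=10-15, equal or worse at n=20, and equal or better from n=25.

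The SAP also states that small risk sets occur at both ends, and the table footnote names the method. A reader might infer that the late effect is concealed; the documents do not support that. What they lack is any count of the events left out. N at risk shows that few patients remain, not that progressions among them were ignored.

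A reader might also infer that the threshold should be confined to the start of the curve. That does not follow. From n=15, with up to 50% prevalent, such a rule behaves like the unmodified estimator and gives up the variance gain. It leaves bias when most patients are prevalent (0.30 at n=15 with 90% prevalent). Written into 5.5.1, it would also change OS and targeted versus other, where no problem is shown.

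The protocol's condition on subgroup size would be a safeguard, and the SAP says that it is consistent with the protocol. But SAP 5.5.1 lists the other-treatment estimates without that condition.

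**Conclusion.** The point holds for PFS in Table 14.2.1.4, as a conditional statement. Mean 24-month PFS is overstated if a subgroup has about 20 patients or fewer and PFS is short. At a median of 11 months the excess is roughly 2-13 points at n=20 (0.24-0.35 against 0.22), 8-19 at n=15 and 24-38 at n=10. With long PFS it is negligible at n=20 but not at n=10. The direction is arithmetic; the size rests wholly on assumed inputs.

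It should not be read as a forecast that the reported rates will be too high: actual sizes and PFS are unknown, and a single estimate can still fall below the truth. Everolimus and sunitinib, at 35 or more, are affected only if PFS is very short or censoring heavy. No claim is made for OS or for targeted versus other; for the latter, the SAP also lists "Table 14.2.2.9.1: Analysis of Progression-Free Survival – Reference Set – Overall and Targeted Therapies Vs Other Treatments Group", with its estimator unstated. The main all-patient analysis uses the unmodified estimator and is untouched.

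**What to change.** Keep the Lai and Ying estimate. In PFS Table 14.2.1.4, and in 14.2.1.3 for consistency, print beside it:

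- the unmodified left-truncated Kaplan-Meier 24-month rate and median, each with 95% CI, from PROC PHREG;
- the number of events that the threshold ignored.

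In SAP 5.5.1, align the sentence on portions of the curve with the formula, so that events at Y=5 are counted. Restore the protocol's condition that other-treatment subgroup estimates are given only where numbers suffice.

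The cost is one extra column and one count per table, plus two edits to the text. PROC PHREG with left truncation is already planned in 5.5.1 for all patients and in 5.9.7 for other subgroups. The drawback is that the added estimate is somewhat more variable at n=20-35, which its confidence interval will show.
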